6.1.2.2 Clinical Laboratory Tests

The following safety laboratory parameters will be measured according to the schedule in section 11:

- **Clinical chemistry:** Potassium, sodium, urea, creatinine, uric acid, calcium, protein, albumin, total bilirubin, alkaline phosphatase (ALP), gamma glutamyl transferase (GGT), aspartate aminotransferase (AST), alanine aminotransferase (ALT) and glucose
- **Hematology:** white blood cell count, red blood cell count, hemoglobin, hematocrit, mean corpuscular volume, mean corpuscular hemoglobin, mean corpuscular hemoglobin concentration, absolute differential count (neutrophils, lymphocytes, monocytes, eosinophils and basophils) and platelets
- **Urinalysis:** Glucose, bilirubin, ketone, specific gravity, blood, pH, protein, urobilinogen, nitrite and leucocytes
- **Serology:** human immunodeficiency virus (HIV), Hepatitis B and Hepatitis C
- **Drugs of abuse:** amphetamines, barbiturates, benzodiazepines, cocaine, opiates, phencyclidine (phenylcyclohexalpipерidine), tetrahydrocannabinol, methadone, methamphetamine, tricyclic antidepressants, oxycodone, propoxyphene, cotinine, and alcohol breath test

6.1.2.3 Vital Signs

The following vital signs measurements will be obtained according to the schedule in section 11:

- Systolic blood pressure (SBP) [mmHg]
- Diastolic blood pressure (DBP) [mmHg]
- Pulse rate (bpm)
- Body temperature (oral) [°C]

6.1.2.4 Electrocardiograms

Standard 12-lead ECG will be performed according to the schedule in section 11.

The ECG will be evaluated by the Investigator as ‘Normal’, ‘Abnormal, NCS’ or ‘Abnormal, CS’.

[REDACTED] International
Statistical Analysis Plan

6.1.2.5 Physical Examination

A full physical examination will be performed according to the schedule in section 11 at screening. At the discretion of the Principal Investigator, a follow-up physical examination will be performed on subjects withdrawn from the study due to an AE. Findings will be listed by body system, including skin evaluation.

[REDACTED]

[REDACTED]

[REDACTED]	[REDACTED]
[REDACTED]	[REDACTED]
[REDACTED]	[REDACTED]
[REDACTED]	[REDACTED]
[REDACTED]	[REDACTED]
[REDACTED]	[REDACTED]
[REDACTED]	[REDACTED]
[REDACTED]	[REDACTED]
[REDACTED]	[REDACTED]
[REDACTED]	[REDACTED]
[REDACTED]	[REDACTED]
[REDACTED]	[REDACTED]
[REDACTED]	[REDACTED]
[REDACTED]	[REDACTED]
[REDACTED]	[REDACTED]
[REDACTED]	[REDACTED]
[REDACTED]	[REDACTED]
[REDACTED]	[REDACTED]
[REDACTED]	[REDACTED]
[REDACTED]	[REDACTED]
[REDACTED]	[REDACTED]
[REDACTED]	[REDACTED]
[REDACTED]	[REDACTED]

[REDACTED]

6.1.2.7 Overall Assessment of Tolerability

The patient will assess the overall tolerability of the trial treatment on a 4-point verbal rating scale by answering the question: "How would you rate the overall tolerability of the study medication?" (0 = poor; 1 = fair; 2 = good; 3 = very good). The Investigator should make the corresponding assessment at about the same time as the patient. Assessments should be made independently from each other, i.e.,

[Redacted] International
Statistical Analysis Plan

without knowing the other's assessment result when making the assessment. Assessments will be performed according to the schedule in section 11.

6.1.2.8 *Inspection of IMP application sites*

Inspection of IMP application sites will be done at screening, before every IMP administration and post-dose at 1 and 6 (± 9) hours on Day 1 and Day 7, respectively. On Days 2 to 5 inspections will be done before IMP administration during the morning visit to the clinic (subjects will still be in the clinic the morning of Day 2) and on Day 6 inspection will be done before IMP administration, in the morning and evening, respectively.

6.1.2.9 *Concomitant Medication*

Concomitant medication will be coded using the World Health Organisation-Drug Dictionary (WHO-DD) (Version WHODDE MAR 2017) and will be classified by Anatomical Therapeutic Chemical (ATC) categories.

6.1.3 *Pharmacokinetics Variables*

6.1.3.1 *Pharmacokinetic Parameters*

Unless otherwise stated, derivation of pharmacokinetic (PK) parameters will be the responsibility of Quantitative Clinical Development (QCD), [Redacted] International. The following PK parameters will be determined for diclofenac in plasma following single dose administration:

[Redacted]

[Redacted]	[Redacted]
[Redacted]	[Redacted]
[Redacted]	[Redacted]

[REDACTED] International
Statistical Analysis Plan

The following pharmacokinetic (PK) parameters will be calculated for Diclofenac in plasma following multiple dose administration:

Table 4 PK Parameters after Multiple Dose Administration for Diclofenac

Parameter	Definition
[REDACTED]	[REDACTED]
$C_{max,ss}$	[1] Maximum observed concentration at steady state (Day 7)
$t_{max,ss}$	[2] Time corresponding to occurrence of $C_{max,ss}$ at steady state
[REDACTED]	[REDACTED]
$AUC_{(0-\tau,ss)}$	[1] AUC over one dosing interval at steady state (Day 7)
[REDACTED]	[REDACTED]
$C_{av,ss}$	[2] Average concentration at steady state (Day 7)
%PTF	[2] Percentage Peak trough fluctuation

[1] primary endpoints; [2] secondary endpoints

[REDACTED]	[REDACTED]
[REDACTED]	[REDACTED]
[REDACTED]	[REDACTED]
[REDACTED]	[REDACTED]
[REDACTED]	[REDACTED]
[REDACTED]	[REDACTED]
[REDACTED]	[REDACTED]
[REDACTED]	[REDACTED]
[REDACTED]	[REDACTED]
[REDACTED]	[REDACTED]
[REDACTED]	[REDACTED]
[REDACTED]	[REDACTED]
[REDACTED]	[REDACTED]

[REDACTED] International
Statistical Analysis Plan

6.1.3.2 Pharmacokinetic Parameter Calculation Methods

Diclofenac [REDACTED] PK parameters will be calculated by non-compartmental analysis methods from the concentration-time data using WinNonlin (WNL) Professional (Version 6.3) following these guidelines:

- Actual sampling times relative to dosing rather than nominal times will be used in the calculation of all derived PK parameters.
- There will be no imputation of missing data.
- Any subjects with missing concentration data will be included in the PK analysis set provided that at least $C_{max,ss}$ and $AUC_{(0-\tau,ss)}$ can be reliably calculated.
- For subjects with pre-morning-dose plasma concentrations on Day 1 in each treatment period, the subject's data may be included without any adjustments in PK parameter derivation for that period, if the pre-dose concentration is $\leq 5\%$ of the individual's maximum observed plasma concentration (C_{max}). If the pre-dose value is $> 5\%$ of C_{max} , the subject's data will be excluded from all bioavailability evaluations.
- For first dose, Day1, parameters, all below the lower limit of quantification (BLQ) values pre-dose and in the absorption phase prior to the first quantifiable concentration will be substituted by zeros. Thereafter BLQ values between evaluable concentrations will be substituted by missing, before the calculation of the PK variables. Terminal BLQ values will be disregarded.
- For dosing Days 5 to 7, BLQ values pre-dose, in the absorption phase, and between evaluable concentrations will be substituted by missing, before the calculation of the PK variables. Terminal BLQ values will be disregarded.

PK parameters will be estimated according to the following guidelines:

- [REDACTED]
- [REDACTED]
- [REDACTED]
- [REDACTED]

[REDACTED] International
Statistical Analysis Plan

[REDACTED]

Guidelines for multiple dose, Day 7

- $C_{max,ss}$ at steady state will be obtained directly from the concentration-time data.

[REDACTED]

- $t_{max,ss}$ time at which $C_{max,ss}$ occurs at steady state.

[REDACTED]

[REDACTED]

[REDACTED]

[REDACTED]

[REDACTED]

- AUC is calculated as follows:

- The linear trapezoidal method will be employed for all incremental trapezoids arising from increasing concentrations and the logarithmic trapezoidal method will be used for those arising from decreasing concentrations.

[REDACTED]

[REDACTED]

- $AUC_{(0-\tau),ss}$ Area under the concentration-time curve over the dosing interval.

- $C_{av,ss}$ Average steady-state concentration calculated as $AUC_{(0-\tau),ss}/\tau$.

International Statistical Analysis Plan

The following PK parameters will also be derived using SAS (version 9.3 or higher).

- PTF Peak trough fluctuation calculated as $100\% * (C_{\max,ss} - C_{\text{pre},ss}) / C_{\text{av},ss}$.

6.2 Analysis Populations

6.2.1 Safety Population

All subjects who received at least one dose of IMP will be included in the safety analysis for the study.

6.2.2 Pharmacokinetic Population

The PK population will consist of all subjects in the safety population for whom at least one of area under the plasma concentration-time curve over one dosing interval ($AUC_{(0-\tau,ss)}$ [$\tau = 12$ hours]) or maximum steady-state plasma drug concentration during a dosage interval ($C_{\max,ss}$) can be calculated for one treatment and who have no major protocol deviations thought to have impact on the analysis of the PK data.

Additionally, samples with relevant time deviations may be excluded from statistical analysis.

Any data excluded will be discussed in the CSR.

6.3 Statistical Analysis Methods

6.3.1 Listings and Descriptive Statistics

All original and derived parameters as well as population characteristics will be listed and described using summary statistics. Frequency counts (number of subjects [n] and percentages) will be made for each qualitative variable. Descriptive statistics (n, mean, standard deviation [SD], median, minimum and maximum) will be calculated for each quantitative variable (unless otherwise stated). All listings will include repeated and unscheduled measurements.

The following rules will apply to any repeated measurements:

- If the repeated measurement occurs prior to the first dose of study drug then the last obtained value of any repeated measurement will be used in the descriptive statistics.
- If the repeated measurement occurs after the first dose of study drug then the original value of any repeated measurements will be used in the descriptive statistics.

International Statistical Analysis Plan

All descriptive statistics will be presented by treatment for measurements obtained during each treatment period. The baseline for all measurements (where applicable) will be the last pre-dose measurement within each period. Descriptive statistics for all data obtained at Screening and follow-up will be presented separately.

If a log-transformation of data is required the natural logarithm will be taken unless otherwise stated.

6.3.2 Rounding and Decimal Places

- The following rules will be followed with regards to the number of decimal places and presentation of data in the tables and listings of diclofenac and capsaicin (data permitting) PK concentration data:
 - The individual concentrations will be reported to the same precision as the source data (for example, if the source data is presented to five significant digits, the individual values will be presented to five significant digits)
 - The mean, SD, geometric mean and median will be tabulated to one more significant digit compared to the source data.
 - Minimum and maximum values will be tabulated to the same precision as the source data.
 - Geometric CV% will be presented to two decimal places.
- The following rules will be followed with regards to the number of decimal places and presentation of data in the tables and listings of diclofenac and capsaicin (data permitting) PK parameters:
 - Individual PK parameters will be presented to three significant digits, with the exception of [REDACTED] which will be presented to two decimal places. In addition, parameters directly derived from source data (e.g. C_{max}) shall be reported with the same precision as the source data
 - The mean, gMean, median and SD values will be reported to one more significant digit than the source data, except for CV% which will be presented to two decimal places. For [REDACTED] the median, minimum and maximum will be presented to two decimal places

[REDACTED] International
Statistical Analysis Plan

- Geometric least squares means from the statistical analysis will be presented to three significant digits
- Estimates and confidence intervals in the form of percentages will be presented to two decimal places

6.3.3 Statistical Significance Level

All statistical tests will be two-sided and will be performed at the 5% level of significance, unless otherwise stated. All CI will be two-sided 90% Confidence intervals.

6.3.4 Software

All statistical analyses will be performed using Statistical Analysis Software (SAS[®]) Version 9.3 or later [2]. The PK analysis will be performed using WinNonlin Professional Software Version 6.3 or later [3].

6.3.5 Missing Data

There will be no imputation of missing data.

Concentration data identified with no valid result (NOR) or not analyzed (NOA) are not considered in the evaluation (graphs and calculations). However, they are listed in the respective tables of the CSR. For handling of BLQ PK concentrations in non-compartmental analysis see section 6.1.3.2. For handling of BLQ PK concentrations in listings and summaries see section 6.3.11.1.

6.3.6 Interim Analysis

Not applicable.

6.3.7 Protocol Deviations

All protocol deviations will be recorded by the Investigator and will be listed by subject and will include a description of the deviation, the data/time of the deviation (if available), study day of the deviation, time point (if applicable). Protocol deviations will be reported based on the safety population.

All protocol deviations will be discussed between [REDACTED] (physician, Data Manager, Biostatistician and PK Scientist/Analyst) and also the Sponsor during the Data Review Meeting (DRM) before

[REDACTED] International
Statistical Analysis Plan

database lock. Protocol deviations will be classified as major or minor. Exclusion/inclusion of subjects from analysis populations (see 6.2) based on the deviations will be decided upon at the DRM. The classifications and further characteristics will be specified in a separate document (Protocol Deviation Specifications dated 20 Jul 2017), the protocol deviations specification. The main categories for protocol deviations that will be considered are described in the following table.

Table 6 Protocol Deviations Categories

Code	Category
INEX	Subject did not meet the inclusion/exclusion criteria
CM	Subject received prohibited concomitant medications
DOSE	Subject did not receive the planned dose
TIME	Deviations from scheduled procedure time outside of the window allowance
PROCEDURE	Procedures not performed due to error or subject availability
PROCESS	Deviations regarding sample processing
ICF	Use of the incorrect ICF, ICF incorrect, etc.
OTHER	Any deviation that does not fit into one of the categories listed above

The window allowance document (WAD, version 1, 28Mar2017) will stipulate the tolerance windows for safety and PK assessments. Measurements performed within these tolerance windows will not be considered as protocol deviations and will not be reported.

6.3.8 Demographic Data

All demographic data will be presented using the safety population. Demographic characteristics will be summarized (n, mean, SD, minimum and maximum for age and BMI; and frequency counts and percentages for race, and sex).

6.3.9 Concomitant Medication

Prior and concomitant medication will be coded and listed using the safety population. Concomitant medication is a medication that is taken after 2 weeks before the first administration of the IMP is taken and during the study up to the follow-up visit or the subject withdraws from the study. Prior medications will be listed first for all subjects followed by all concomitant medications.

[REDACTED] International
Statistical Analysis Plan

6.3.10 Exposure to the Investigational Medicinal Product

Exposure to the IMPs will be shown in a listing, including weight of the tube before and after dosing. The dose will be calculated from the difference in tube weights (g) and the percentage content of diclofenac and capsaicin:

$$\text{Dose}_{\text{diclofenac}} [\text{mg}] = (\text{Tube weight difference} * 1000 [\text{mg}]) * 0.02 \quad \text{for test products 1(A) and 2(B)}$$

$$\text{Dose}_{\text{diclofenac}} [\text{mg}] = (\text{Tube weight difference} * 1000 [\text{mg}]) * 0.0232 \quad \text{for reference product C}$$

$$\text{Dose}_{\text{capsaicin}} [\text{mg}] = (\text{Tube weight difference} * 1000 [\text{mg}]) * 0.00075 \quad \text{for test product 2(B)}$$

Afternoon tube weights not available in the database will be imputed by using the previous and the subsequent weights.

A table will summarize per subject dosing variables: the number of actual doses, the dose of diclofenac and capsaicin per administration, the cumulative dose, the number of days as well as the total dose over all subjects by treatment and overall in the study.

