The study population for this study will be stratified 50:50 (Caucasians versus Black People) and subjects who meet the inclusion criteria will be considered eligible to participate in the study.

Inclusion Criteria:

1. Healthy males and females, 18 to 50 years (inclusive) at time of screening.
2. Body mass index between 18.5 and 29.9 kg/m² (inclusive).
3. Body mass not less than 50 kg for males and females.
4. Findings for medical history, vital signs, physical examination, standard 12-lead electrocardiogram (ECG) and laboratory investigations must be normal or within laboratory reference ranges for the relevant laboratory tests, unless the Principal Investigator (PI) considers the deviation to be not clinically significant for the purpose of the study.
5. Non-smokers.
6. Females, if:
 - Not of childbearing potential, e.g., has been surgically sterilized, undergone a hysterectomy, amenorrhea for ≥ 12 months and considered post-menopausal.
Note: In post-menopausal women, the value of the serum pregnancy test may be slightly increased. This test will be repeated to confirm the results. If there is no increase indicative of pregnancy, the female will be included in the study.
 - Of childbearing potential, the following conditions are to be met:
 - Negative pregnancy test
 - If this test is positive, the subject will be excluded from the study. In the rare circumstance that a pregnancy is discovered after the subject received the IMP; every attempt must be made to follow her to term
 - Not lactating
 - Abstaining from sexual activity (if this is the usual lifestyle of the subject) or must agree to use an accepted method of contraception, and agree to continue with the same method throughout the study
 - In this study the concomitant use of hormonal contraceptives is allowed
 - Examples of reliable methods of contraception include oral (documented that the dose has been stable for at least one month before the first intake of the IMP), injectable or implantable contraceptives, non-hormonal/hormonal intrauterine device, and barrier methods combined with an additional contraceptive method
 - Other methods, if considered by the PI as reliable, will be accepted
7. Written informed consent given for participation in the study.

Investigational Medicinal Products*Test Product 1(A)*

Generic name	:	Diclofenac sodium
Trade name	:	Diclofenac mono gel 2%
Dosage form	:	Immediate release topical gel
Dose	:	Multiple doses (2 g, bid) of Diclofenac 2%

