Route of administration	:	Topical
Manufacturer	:	Boehringer Ingelheim Pharma GmbH & Co. KG
Country of origin	:	Germany

Test Product 2 (B)

Generic name	:	Diclofenac + Capsaicin
--------------	---	------------------------

Boehringer Ingelheim Pharma GmbH & Co. KG
Combination of Diclofenac 2% + Capsaicin 0.075%

Product name	:	Combination of Diclofenac 2% + Capsaicin 0.075% formulation
Dosage form	:	Immediate release topical gel
Dose	:	Multiple doses (2 g, bid) of Diclofenac 2% + Capsaicin 0.075%
Route of administration	:	Topical
Manufacturer	:	Boehringer Ingelheim Pharma GmbH & Co. KG
Country of origin	:	Germany
Reference Product (C)		
Generic name	:	Diclofenac sodium topical gel
Trade name	:	Voltarol® 12 Hour Emulgel 2.32% Gel
Dosage form	:	Immediate release topical gel
Dose	:	Multiple doses (2 g, bid) of Voltarol (Diclofenac sodium 2.32%)
Route of administration	:	Topical
Manufacturer	:	Novartis Consumer Health UK Ltd.
Country of origin	:	United Kingdom
Analytes		
Diclofenac and capsaicin		
Sample Size		
Up to 48 eligible subjects (stratified 50:50 Caucasian versus Black people) will be enrolled into the study, to complete the study with at least 42 evaluable subjects.		
Pharmacokinetic Endpoints		
Primary and secondary endpoints are only calculated for diclofenac.		
Primary Pharmacokinetic Endpoints:		

 • Area under the plasma concentration-time curve (AUC) over one dosing interval ($\tau = 12$ hours) ($AUC_{0-\tau,ss}$) (Day 7) • Maximum plasma drug concentration during a dosage interval ($C_{max,ss}$) obtained directly from the concentration-time data (Day 7) 		
Secondary Pharmacokinetic Endpoints:		

 • Time to maximum observed plasma concentration at steady state ($t_{max,ss}$) (Day 7) • Average plasma concentration ($C_{av,ss}$) calculated as $AUC_{0-\tau,ss}/\tau$, τ is one dosing interval (12 hours) • Percentage peak-trough fluctuation (%PTF), calculated as $[100*(C_{max,ss} - C_{pre,ss})/C_{av,ss}]$ 		

Safety Variables (other endpoints)

Safety variables will include vital signs, 12-lead ECG, hematology, clinical chemistry, pregnancy test results, overall assessment of tolerability [REDACTED] Adverse events (AEs) and concomitant medication will also be reported.

Statistical Analysis*Pharmacokinetic population:*

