2 QUALITATIVE AND QUANTITATIVE COMPOSITION

Diethylammonium-{-o-[2,6-dichlorophenyl]-amino]-phenyl}-acetate.

100g of Voltarol® 12 Hour Emulgel 2.32% Gel contains 2.32g of the active substance diclofenac diethylammonium, which corresponds to 2g diclofenac sodium.

Excipients: Propylene glycol (50 mg/g gel)
Buthylhydroxytoluene (0.2 mg/g gel).

For the full list of excipients, see section 6.1

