4.9 Overdose

The low systemic absorption of topical diclofenac renders overdose very unlikely.

However undesirable effects, similar to those observed following an overdose of Voltarol tablets, can be expected if Voltarol[®] 12 Hour Emulgel 2.32% Gel is inadvertently ingested (e.g. 1 tube of 50 g contains the equivalent of 1 g diclofenac sodium.)

In the event of accidental ingestion, resulting in significant systemic adverse effects, general therapeutic measures normally adopted to treat poisoning with non-steroidal anti-inflammatory medicines should be used. Gastric lavage and the use of activated charcoal should be considered, especially within a short time of ingestion.

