2. STUDY DESIGN

This will be a multiple-dose, open-label, randomized, 3-period, 3-treatment, 6 sequence (3x3x6) crossover study with topically administered diclofenac 2% (2 g) in the presence and absence of capsaicin 0.075%, in at least 42 healthy male and female subjects (stratified 50:50 Caucasian versus Black people) in a single study center.

Details on the medicinal products can be found in Section 8.2 in the CSP. For details relevant for the statistical evaluation please refer to Section 6.3.12 of this SAP.

The study will comprise:

- Screening period of maximum 21 days.
- Three-treatment periods (each of which will include a multiple-dose period of 7 days [twice daily and only in the morning on Day 7] and two PK profile periods of 12 hours [Day 1] and 24 hours [Day 7]) separated by a wash out period of at least 7 calendar days between the last administration of the Investigational medical product (IMP) in a treatment period and the first administration of IMP in the next treatment period. Clinic stay/visits will be as follows:
 - Subjects will be admitted to the study center on Day -1 and leave the center after the morning dose on Day 2, at least 24 hours after the initial dosing on Day 1
 - Subjects will visit the study center on Days 3 and 4 for the morning dose
 - On Day 5, they will visit the center for PK blood sampling prior to morning and evening dose and will be re-admitted to the study center on the evening of Day 5
 - Subjects will leave the center at least 24 hours after the morning dose on Day 7
- A follow-up visit will occur within 72 hours after completion of the last treatment period of the study.

Before the first administration of IMPs subjects will be randomized to one of 6 treatment sequences stratified by race (Black, Caucasian), i.e., 4 Black and 4 Caucasian subjects will be assigned to each treatment sequence.

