6.3.12 Assessment of Relative Bioavailability

6.3.12.1 Main Analysis

Relative bioavailability will be estimated for the primary diclofenac PK parameters (Table 4) by the ratios of the gMeans (test/reference [T/R]) for AUC(0- τ ,ss) and C_{max,ss} at steady state (refer to 6.1.3 and [4]). Additionally, their two-sided 90% CIs will be provided.

The statistical model will be an analysis of variance (ANOVA) on the logarithmic scale including fixed effects for sequence, subject nested within sequence, period and treatment. Only the data for the comparison under investigation will be included in the statistical analysis (i.e., when comparing Test Product 2 and Reference, the data for the Test Product 1 will be removed from the dataset), only subjects with data for both products will be retained in the analysis. These methods are in line with the EMA guideline [4].

For each endpoint, the difference between the expected means for log(T)-log(R) will be estimated by the difference in the corresponding adjusted means (Least Squares Means). 90% CIs for the difference will be calculated based on the residual error from ANOVA. Least squares means will be tabulated with 90% CIs. The differences between the test and reference product and the CIs will be back-transformed to the original scale.

The following comparisons will apply:

- Test Product 2 (B) vs Reference (C)
 - i.e. B: Diclofenac + Capsaicin versus C: Diclofenac sodium topical gel (Voltarol®)
- Test Product 2 (B) vs Test Product 1 (A)
 - i.e. B: Diclofenac + Capsaicin versus A: Diclofenac sodium

[REDACTED]

[REDACTED]

[REDACTED]

[REDACTED]

[REDACTED] International
Statistical Analysis Plan

[REDACTED]

The treatment group labels that will be used in the TLFs are defined in a separate document (Table, Listing and Figure Shells).

The following SAS code will form the basis of the analysis:

```
PROC MIXED;  
    CLASS treatment_code period sequence subject;  
    MODEL var=treatment_code sequence period subject(sequence);  
    /*where var= log transformed primary PK endpoints*/  
    LSMEANS treatment_code / PDIF CL ALPHA=0.1;  
    ODS OUTPUT LSMEANS = ls_means;  
QUIT;
```

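### SAP 6.3.10 computes the diclofenac dose on two salt bases, so exposure to the reference gel is reported 16% too high on the sodium basis; no visible T/R analysis is affected

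*SAP*

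**What the plan says.** SAP 6.3.10 defines the exposure variable: "The dose will be calculated from the difference in tube weights (g) and the percentage content of diclofenac and capsaicin". The formulas under that sentence take tube weight difference in mg times 0.02 for A and B, and times 0.0232 for C. The result feeds the exposure listing (16.2.5:1) and the exposure table (15.1.5:1), as dose per administration, cumulative dose and total by treatment.

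The SPC reproduced in protocol Appendix 15.1 gives the composition of C. Its section 2 says that 100 g of gel holds 2.32 g of the diethylammonium salt, "which corresponds to 2g diclofenac sodium". Its section 4.9 agrees: "1 tube of 50 g contains the equivalent of 1 g diclofenac sodium".

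The product descriptions elsewhere differ from this:

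- The protocol synopsis describes C's dose as "Multiple doses (2 g, bid) of Voltarol (Diclofenac sodium 2.32"%), and protocol 8.2 does the same. Both call the 2.32% sodium.
- For A the generic name is diclofenac sodium and the dose line reads "Multiple doses (2 g, bid) of Diclofenac 2"%.
- For B neither place names the salt.
- SAP 6.3.12.1 labels the comparisons "B: Diclofenac + Capsaicin versus C: Diclofenac sodium topical gel" and "B: Diclofenac + Capsaicin versus A: Diclofenac sodium", so it also treats C as a sodium product.
- SAP 2 sends the reader back to the protocol table: "Details on the medicinal products can be found in Section 8.2 in the CSP".

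SAP Addendum 2.3 states that diclofenac content differs between the products (2% against 2.32%). It uses this as the reason to normalise by gel weight and not by dose.

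**The concern.** A single variable should have a single unit of substance. Here a milligram means diclofenac sodium for A, but diclofenac diethylammonium for C. Nothing in the SAP declares the second basis, and the product names in the SAP and protocol lead the reader to take 0.0232 as sodium.

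Followed as written, the exposure outputs would show subjects receiving 16% more diclofenac from C than from A for the same weight of gel. By the protocol's own appendix the two contents are equal on either salt basis. In a relative bioavailability study, a reader could use that apparent difference in dose to explain a T/R ratio. The same premise already appears in Addendum 2.3.

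**Working it through.** **Inputs**

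- Factors: 0.02 (A, B) and 0.0232 (C), SAP 6.3.10.
- Salt equivalence for C: 2.32 g diethylammonium = 2 g sodium per 100 g gel, Appendix 15.1, SPC section 2.
- Stated tube content for C: 1 g sodium equivalent per 50 g, SPC section 4.9.
- Gel weight: 2 g planned; 1 to 5.1 g observed, Addendum 2.3.
- Applications per period: twice daily on Days 1 to 6 and once on Day 7, so 6 × 2 + 1 = 13.

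**Which factor is on the sodium basis?** The SPC's own figure tests this.

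- 50 g × 0.02 = 1.00 g, which reproduces the stated 1 g.
- 50 g × 0.0232 = 1.16 g, which does not; it is the mass of the diethylammonium salt.

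The sodium factor for C is therefore 0.0232 × 2/2.32 = 0.02.

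**Size for C.** Dose (mg) = gel weight (g) × 1000 × factor. The ratio is 0.0232/0.02 = 1.16 at any gel weight.

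| Gel of C | SAP formula (mg) | Sodium equivalent (mg) | Excess (mg) |
|---|---|---|---|
| 1 g | 23.2 | 20.0 | 3.2 |
| 2 g (planned) | 46.4 | 40.0 | 6.4 |
| 5.1 g | 118.3 | 102.0 | 16.3 |
| 13 × 2 g (one period) | 603.2 | 520.0 | 83.2 |

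The 1 g and 5.1 g rows are illustrative, because the Addendum does not give the observed range by product. The last row assumes 13 applications of exactly 2 g.

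**C against A at 2 g of gel**

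- As planned: 46.4/40.0 = 1.16.
- Both as sodium: 40.0/40.0 = 1.00.
- Both as diethylammonium: A becomes 40.0 × 2.32/2 = 46.4 mg, so 46.4/46.4 = 1.00.

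**B, salt not stated (both cases assumed)**

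- If its 2% is sodium, B is on the same basis as A, and only C is off.
- If its 2% is diethylammonium, 40.0 mg is 40.0/1.16 = 34.5 mg sodium equivalent, and B would also be 16% too high.

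**Does the factor reach the T/R analyses?** The model in SAP 6.3.12.1 takes log AUC and log Cmax at steady state with sequence, subject within sequence, period and treatment; dose does not enter. Addendum 2.3 divides by grams of gel. Only normalisation by the calculated dose would bring the factor in. It would multiply B/C by (1/0.02)/(1/0.0232) = 1.16, and the Addendum says that this normalisation is not intended.

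**The case against.** The strongest reply is that no sum is wrong. The SAP says it uses percentage content, and 2.32% is the true content of what the SPC calls the active substance. On a diethylammonium basis C is correct and A is too low, so calling C's figure the error presumes the sodium basis. The SAP also follows the protocol's product table faithfully; the direct contradiction is between that table and Appendix 15.1. This stands as a description of where the error started. It does not rescue the variable, because on either basis one of A and C is wrong relative to the other and no text declares the change of basis.

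The practical effect is also small. Addendum 2.1 adds a tube weight difference column to the listing and a Day 7 gel weight summary to the table. Both are independent of salt and allow a correct comparison. It also drops the overall-study summary statistics, where the bases would have been pooled. That limits the consequence, but the mg figures for C would still be reported. The Addendum further adds the name diclofenac to the column labels for A and the reference; that label names no salt, so it does not cure the mismatch. The table shells are a separate document and may say more.

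Two cautions hold. That A's 2% is the weight of the sodium salt is read from its generic name; the dose line itself says only diclofenac. And protocol 7.1.1 describes one 2% diclofenac given with and without capsaicin, which points to the same salt in A and B but does not state it.

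**Conclusion.** The concern holds as a minor error in exposure reporting. C's reported dose is 16% above its own sodium equivalent, and this follows from Appendix 15.1 alone. That A and C have equal content rests additionally on reading A's 2% as diclofenac sodium, as its generic name indicates. The basis for B cannot be checked until its salt is stated.

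The visible T/R ratios, their 90% confidence intervals and the gel-normalised analyses are unaffected. Parts of SAP 6.3.12 are redacted, so this statement is limited to what can be seen. The Addendum 2.3 sentence on differing content does not hold for A against C on one salt basis, and is unverified for the planned comparison B against C. Gel-weight normalisation remains usable in either case.

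**What to change.** - In SAP 6.3.10, express all products on one stated salt basis using the Appendix 15.1 equivalence, and name that basis in Listing 16.2.5:1 and Table 15.1.5:1. Alternatively, keep 0.0232 and label C's figure explicitly as diclofenac diethylammonium.
- State the salt of B.
- Reconcile the description of C in the protocol synopsis and section 8.2, and the matching label in SAP 6.3.12.1, with Appendix 15.1.
- Qualify the content statement in Addendum 2.3 for A against C, and correct it for B against C if B is sodium. Leave the normalisation by gel weight as it is.

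The cost is one constant or label in the exposure program and a few sentences of text. It needs no new data, no rerun of the bioavailability analysis and no change to what was administered.
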